2.4.3 Rationale for Dose Selection

ABBV-4083, albendazole, and ivermectin or matching placebo will be administered orally.

The 400 mg QD dose of ABBV-4083 administered for 7 or 14 days was tested in the FIH study (Study M16-710) and was considered safe and well tolerated. This dose maintains mean free plasma concentrations of ABBV-4083 in excess of the estimated in vitro EC_{90} for a similar period of time as a dose in jirds (50 mg/kg) that is effective following 7 or 14 days of dosing in *Litomosoides sigmodontis* infected jirds. This dose also produces a similar mean free C_{max} and longer time in excess of the in vitro EC_{90} compared to a dose in jirds (20 mg/kg) that is effective

following 7 days of dosing in combination with albendazole in *Litomosoides sigmodontis* infected jirds.

The oral dose of albendazole over-encapsulated tablets to be administered to subjects in Arms C, D and E is 400 mg QD for 7 days, 3 days and 7 days, respectively. Albendazole is given at 400 mg QD for 1 to 3 days for intestinal worms and skin nematodes such as cutaneous *larva migrans*, and at 400 mg BID for 1 to 3 days for liver flukes.⁵⁷

Higher daily doses (400 mg BID) for prolonged periods up to 84 days total are indicated for more disseminated systemic infections such as echinococcosis and neurocysticercosis.⁵⁸ Since mild to moderate elevations of liver enzymes have been reported with the higher/more prolonged dose,⁵⁸ and the 400 mg QD dose produces plasma exposure of the active metabolite (albendazole sulfoxide) roughly equivalent to the exposure shown to be active in combination with ABBV-4083 in preclinical efficacy studies, this dose was selected for combination with ABBV-4083. In the preclinical *Litomosoides sigmodontis* model in jirds, as few as 3 days of albendazole combined with 7 days of ABBV-4083 produced strong signals of *Wolbachia* depletion and female adult worm sterilisation,⁵⁹ providing the basis for the duration of dosing in Arm D. Plasma concentrations of albendazole sulfoxide are increased by administration with food,^{60,61} therefore albendazole will be administered with food in this study.

Ivermectin over-encapsulated tablets will be given at the standard MDA dose as a single oral dose of 150 µg/kg body weight at Month 6 in Part 2 of the study to subjects who receive ABBV-4083 matching placebo plus albendazole matching placebo. 65,68 Some subjects receiving ABBV-4083 ± albendazole regimens in Part 2 will also receive over-encapsulated ivermectin at Month 6 while the remainder of subjects will receive ivermectin matching placebo, in order to assess the effect of a dose of ivermectin at Month 6 on efficacy at Month 24. No subjects receiving active ABBV-4083 ± albendazole in Part 2 are deemed at significant risk of ocular or other clinical progression without a dose of ivermectin at Month 6, since regimens will only be advanced into Part 2 on the basis of a strong signal of Wolbachia depletion in Part 1. Active anti-Wolbachia treatment is expected to produce a slow decline in skin microfilariae over time due to the sterilisation of adult female worms, lowering the likelihood of the appearance of ocular microfilariae. In addition, studies have shown that ocular disease progression is slow and is highly associated with microfilarial invasion into the eyes. Frequent ophthalmological examinations will be conducted, and unblinded ivermectin will be provided as rescue therapy at the discretion of the Investigator. Therefore, the study plan provides adequate measures to ensure the safety of all subjects in Part 2 who do not receive ivermectin at Month 6.

3 Study Design

3.1 Overall Study Design

DNDi-TYL-01 will be a multicentre, randomised, active and/or placebo-controlled, double-blind, parallel-group, adaptive Phase-II study in two parts. It will be conducted in at least two investigational centres, with competitive recruitment. Additional centres may be included. All centres must however have access to appropriate medical facilities to treat severe AEs.

Part 1 will use a surrogate endpoint of *Wolbachia* depletion in adult female worms to:

• establish proof of concept for ABBV-4083 in onchocerciasis by demonstrating superiority of the regimens of ABBV-4083 alone over the control regimen, albendazole alone, which has been shown to have little or no activity in onchocerciasis, 62,44

- establish the activity of ABBV-4083 and albendazole in combination by demonstrating superiority of a regimen of ABBV-4083 + albendazole over regimens of ABBV-4083 and albendazole alone of equal duration, and
- establish up to two preferred regimens of ABBV-4083 and/or ABBV-4083 + albendazole to progress into Part 2 of the study.

Each subject's participation in Part 1 of the trial will last approximately $6\frac{1}{2}$ months, excluding the screening period, which may be up to 8 weeks. At Month 6, Part 1 will end, and the study will be paused to evaluate the nodules and skin mf. Part 1 data will be unblinded to the Sponsor and analysed to allow for finalisation of the study design in Part 2. Enrolment will then resume in Part 2.

Part 2 will use a clinically relevant endpoint of depletion of skin microfilariae at Month 24 to:

- identify the preferred regimen of ABBV-4083 or ABBV-4083 + albendazole to progress into Phase-III studies, and
- evaluate the effect of a dose of ivermectin 6 months after ABBV-4083 or ABBV-4083 + albendazole on skin microfilarial density at Months 12, 18 and 24.

If the superiority of ABBV-4083 + albendazole over ABBV-4083 alone is not demonstrated in Part 1, surrogate endpoint data from Part 2 (i.e. *Wolbachia* depletion in adult worms at Month 6) from Arms with ABBV-4083 + albendazole and ABBV-4083 alone will be combined with data from Part 1 to assess the superiority of ABBV-4083 + albendazole to ABBV-4083 alone (Part 2 Alternate Scenario).

Each subject's participation in Part 2 of the trial will last approximately 24½ months, excluding the screening period, which may be up to 8 weeks. The set of subjects in Part 2 is fully independent from the set of subjects in Part 1. The final analysis will be conducted at the end of Part 2.

A Safety Review Committee (SRC) and an independent Data and Safety Monitoring Board (DSMB) will be appointed (See Sections 13.2 and 13.3).

3.2 Study Design - Part 1

In Part 1, a total of 150 subjects will be recruited, and will be randomised continuously 1:1:1:1:1 into one of five parallel treatment arms until group size is achieved. Within each treatment arm, participants will be stratified by the number of operable sites with onchocercomata. There will be two strata, i.e. one site and more than one site.

[figure not shown]
The five treatment arms are defined as follows:

- Arm A (N = 30): 7 days of ABBV-4083 400 mg + albendazole matching placebo followed by 7 days of ABBV-4083 matching placebo
- Arm B (N = 30): 7 days of ABBV-4083 400 mg + albendazole matching placebo followed by 7 days of ABBV-4083 400 mg
- Arm C (N = 30): 7 days of ABBV-4083 400 mg + albendazole 400 mg followed by 7 days of ABBV-4083 matching placebo
- Arm D (N = 30): 3 days of ABBV-4083 400 mg + albendazole 400 mg followed by 4 days of ABBV-4083 400 mg + albendazole matching placebo followed by 7 days of ABBV-4083 matching placebo
- Arm E (N = 30): 7 days of ABBV-4083 matching placebo + albendazole 400 mg followed by 7 days of ABBV-4083 matching placebo

Details of timing and sequence of investigations and measures are provided in the Schedule of Events (see Appendix 1). The overall design for Part 1 is presented in Figure 1.

Post-study ivermectin will be given to all participants after nodulectomy at 6 months.

Figure 1. Overall Design for Part 1

4083 = ABBV-4083; Alb = albendazole; d = days; D = (study) day; IVM = ivermectin; M = month; Pbo = placebo

3.3 Study Design - Part 2

For Part 2, up to two treatment arms from Part 1 that are likely to demonstrate high efficacy at Month 24 (based on Part 1 efficacy data and historical studies with doxycycline) and safety will be selected as treatment arms in Part 2. The choice will take into consideration feasibility to use the regimen as potential future treatment.

In order also to assess the effect of a dose of ivermectin at Month 6, participants will be randomised into four treatment arms, with the best candidate based on Part 1 results administered with ivermectin and with ivermectin placebo at Month 6.

Within each treatment arm, subjects will be stratified by the number of operable sites with onchocercomata and by mean screening skin mf. There will be four strata, i.e. 1 site and less than or equal to 5 mf/mg, more than 1 site and less than or equal to 5 mf/mg, 1 site and more than 5 mf/mg, more than 1 site and more than 5 mf/mg.

A total of either 294 subjects (Base Scenario) or 336 subjects (Alternative Scenario) will be recruited. The Base Scenario will be employed:

- if neither Arm C nor Arm D from Part 1 is selected for continued enrolment in Part 2, or
- if either Arm C and/or Arm D in Part 1 is selected for continued enrolment in Part 2 and Arm C and/or Arm D has demonstrated superiority over both Arm E and Arm A in Part 1.

[figure not shown]
The Alternative Scenario will be employed if either Arm C and/or Arm D in Part 1 is selected for continued enrolment in Part 2, but Arm C or Arm D in Part 1 has not demonstrated statistical superiority over both Arm E and Arm A.

In the Base Scenario, subjects will be randomised continuously 2:2:2:1 into one of four parallel treatment arms until group size is achieved:

- Arm K (n = 84): initial treatment with an active regimen selected from Part 1, followed by ivermectin at Month 6;
- Arm L (n = 84): initial treatment with the same active regimen selected from Part 1 as Arm K, followed by ivermectin matching placebo at Month 6;
- Arm M (n = 84): initial treatment with a second active regimen selected from Part 1, followed by either ivermectin or ivermectin matching placebo at Month 6 (decision to be made prior to Part 2);
- Arm N1 (n = 42): initial treatment with ABBV-4083 matching placebo and albendazole matching placebo, followed by ivermectin at Month 6.

Details of timing and sequence of investigations and measures are provided in the Schedule of Events (see Appendix 2). The overall design for Part 2 Base Scenario is presented in Figure 2.

Figure 2. Overall Design for Part 2 - Base Scenario

4083 = ABBV-4083; Alb = albendazole; d = days; D = (study) day; IVM = ivermectin; M = month; Pbo = placebo

In the Alternate Scenario, subjects will be randomised continuously 1:1:1:1 into one of four parallel treatment arms until group size is achieved:

- Arm K (n = 84): initial treatment with an active regimen selected from Part 1, followed by ivermectin at Month 6;
- Arm L (n = 84): initial treatment with the same active regimen selected from Part 1 as Arm K, followed by ivermectin matching placebo at Month 6;
- Arm M (n = 84): initial treatment with a second active regimen selected from Part 1, followed by either ivermectin or ivermectin matching placebo at Month 6 (decision to be made prior to Part 2);

• Arm N2 (n = 84): 7 days of ABBV-4083 400 mg plus appropriate duration of albendazole matching placebo and ABBV-4083 matching placebo followed by either ivermectin or ivermectin matching placebo at Month 6 (decision to be made prior to Part 2).

In the Alternate Scenario, a minimum of 84 subjects with two or more operable sites will be enrolled to allow for approximately 21 subjects per arm to undergo a single-site nodulectomy at Month 6 for the evaluation of *Wolbachia* depletion but still have remaining onchocercomata for evaluation of skin microfilariae and other endpoints at Month 24. The overall design for Part 2 Alternative Scenario is presented in Figure 3.

Post-Study IVM rescue **IVM** Rescue Arm K Arm B. C or D IVM N = 84Arm L Same as Arm K IVM-Pbo N = 84Arm M Arm B. C or D IVM or IVM-Pbo N=84 4083-Pbo x 7d Arm N2 IVM or IVM-Pbo N=84 Alb-Pbo x 7d D6 D13 Screen D0 **M3** M6 M12 M18 M24 Skin snip Skin snip Skin snip Skin snip Skin snip Nodulectomy Nodulectomy (subset) Skin snip (1° endpoint) (Combination rule endpoint)

Figure 3. Overall Design for Part 2 - Alternative Scenario

4083 = ABBV-4083; Alb = albendazole; d = days; D = (study) day; IVM = ivermectin; M = month; Pbo = placebo

Rescue treatment with ivermectin will be offered at the investigator discretion to subjects with clinically significant worsening of symptoms and / or signs related to onchocerciasis at any time during the study or to subjects with increased mean number of microfilariae in the skin at Month 18, compared to the mean number at Month 12.

Post-study ivermectin will be provided after nodulectomy at 24 months to any subject with positive skin and/or eye microfilariae.

3.4 End of Study

The end of study for an individual subject is his or her "last visit" defined as the latest of the following:

- screening failure, or
- the End of Study visit (see Schedules of Events in Appendix 1 and Appendix 2), or
- early termination visit, or
- for subjects lost to follow-up or withdrawn, the last visit the subject attended.

The overall end of the study is defined as the last visit, as defined above, of the last subject.

If a decision is taken to terminate the study early, the study will end when the Sponsor notifies the Investigator, the regulatory authorities and ethics committee(s) in writing that the study has been stopped, or when the "last visit" as defined above occurs for the last subject, whichever is later.

3.5 Assessment and Management of Risks

3.5.1 Risks associated with the IMPs

This section provides information on the main risks identified for the subjects who will take part in the trial, based on protocol design. This list is not exhaustive. Refer also to the ABBV-4083 Investigator Brochure and albendazole or ivermectin reference safety information. 57,58,63-65,68

3.5.1.1 Potential and Identified Risks of ABBV-4083

At this stage of development, there is no risk management plan for ABBV-4083. In the Phase-I study, elevated liver enzymes were seen after single doses of 1000 mg ABBV-4083, but no liver toxicity was seen with multiple doses of ABBV-4083 up to 400 mg QD for 14 days. In addition, no clinically significant haematological laboratory abnormalities associated with AEs or discontinuation from the study were observed (see also Section 2.3.1.1 and Summary of data and guidance to the investigator in the Investigator Brochure). Based on data from preclinical and Phase I studies, a potential risk associated with ABBV-4083 administration is under consideration: "alteration in liver tests". Therefore, monitoring of biochemistry laboratory tests, including liver tests, is required to further assess this potential safety effect during this Phase-II study.

In vitro, ABBV-4083 is metabolised primarily by CYP3A and by cysteine conjugation; codosing with CYP3A inhibitors or inducers may affect ABBV-4083 concentrations. At the 400 mg dose, ABBV-4083 may inhibit P-gp and BCRP.

3.5.1.2 Potential and Identified Risks of Albendazole

Treatment with albendazole has been associated with mild to moderate elevations on hepatic enzymes that usually normalize upon discontinuation of therapy. Cases of acute liver failure of uncertain causality and hepatitis have also been reported. Subjects with abnormal transaminases before starting albendazole therapy should be carefully monitored during treatment. Liver tests should be obtained before the start of therapy and on regular basis for long duration treatment courses.

Treatment with albendazole has been shown to occasionally cause myelosuppression and therefore blood counts should be performed at the start of therapy and regularly for long duration treatment courses. Subjects with liver disease appear to be more susceptible to myelosuppression and warrant closer monitoring.

Treatment with albendazole for neurocysticercosis may cause symptoms associated with an inflammatory reaction following the death of the parasite (e.g. seizures, increased intracranial pressure and focal signs). Pre-existing neurocysticercosis may be also uncovered in patients treated with albendazole for other conditions, especially in areas with high taeniasis infection.

Treatment with albendazole has been shown to be teratogenic and embryotoxic in animal studies. Therefore, women of childbearing age should initiate treatment only after a negative

pregnancy test and should be advised to use highly effective method of contraception up to 1 month after last intake of albendazole. See in addition the albendazole package inserts for further information. 57,64

3.5.1.3 Potential and Identified Risks of the Combination of ABBV-4083 and Albendazole

Results of a GLP-compliant 7-day toxicity study conducted in dogs to examine the effects of ABBV-4083 when dosed in combination with albendazole at exposures comparable to those expected in this clinical trial, no additive effects were seen with the combination. All study findings were non-adverse and reversible by the end of the 28-day recovery period (see Section 2.2.4). However, due to potential risk of alteration of liver tests both with ABBV-4083 or albendazole, the proposed safety monitoring in the study includes transaminases and total bilirubin levels at treatment initiation and frequent monitoring during treatment. Furthermore, the proposed adaptive design of the study, allowing for arms with lower doses of ABBV-4083 if toxicity is observed in initial arms, will mitigate the potential risk of effects on the liver with co-administration of ABBV-4083 + albendazole (see Section 3.5.2.2).

3.5.1.4 Potential and Identified Risks of Ivermectin

Treatment with microfilaricidal drugs such as ivermeetin can produce a systemic inflammatory reaction associated with release of both microfilarial and Wolbachia antigens from dying mf. The so-called Mazzotti reaction is characterised by fever, ocular symptoms, arthralgia, oedema. urticarial rash. pruritus. lymphadenitis. headache. lymphadenopathy, weakness, tachycardia, nausea, conjunctivitis, diarrhoea and vomiting. 52,53 When ivermectin is administered in this study, a Mazzotti reaction may occur. Transient symptoms are likely to occur within 3 days of treatment and are usually mild requiring no more than simple reassurance. In addition, the following possible side effects have been reported with the use of ivermectin: 63,65 allergic reaction, difficulty breathing, acute hepatitis, elevated liver enzymes, elevated blood bilirubin, elevated haemoglobin or elevated eosinophil levels or presence of blood in the urine. When used for treatment of onchocerciasis, worsening of asthma have also been identified. Rarely, transient postural hypotension occurs within 12-24 hours, which responds to rest and oral administration of fluids. ⁶⁸ These symptoms can be managed by the study personnel.

Mazzotti reactions are not expected with ABBV-4083: treatment with an anti-wolbachial agent only interrupts the production of mf, resulting in a slow decline in mf levels. Adult worm death also occurs very slowly (≥ 2 years after treatment), avoiding the potential for inflammation from rapid death of the adult worms.⁵⁰

After administration of repeated doses of ivermectin close to or equal to maternotoxic doses, foetal abnormalities were observed in several animal species. Based on these studies, it is difficult to assess the risk of a single low dose. In clinical studies, no malformations or fetotoxic effects have been attributed to ivermectin. However, follow-up data of exposure to ivermectin during pregnancies is not sufficient to rule out any risk.⁶⁹ Therefore, as a precaution, ivermectin should not be given to pregnant women. Ivermectin is excreted in human milk at low concentrations. Treatment of breastfeeding women should only be undertaken when the risk of delayed treatment to the mother outweighs the possible risk for the newborn.⁶⁵

3.5.2 Adverse Event and Toxicity Management

3.5.2.1 General Management

The following measures will be implemented to minimise the risks:

- Subjects with certain abnormalities on physical or neurological examination or laboratory tests that could interfere with the objectives of the trial or the safety of the subject, in the opinion of the Investigator will be excluded (see Section 6.2), as well as subjects with certain ophthalmological history or conditions;
- Physical examinations, neurological examinations and ophthalmological examinations will be conducted regularly throughout the In-house Periods, and at follow-up visits;
- Blood counts and liver tests including transaminase and bilirubin levels will be monitored regularly during treatment.
- Medications or herbal preparations are prohibited within 14 days prior to IMP intake (see Sections 6.2) and for 24 hours post last intake of the IMP (see Section 8.1) with certain specific exceptions.

3.5.2.2 Toxicity Management and Dose Adjustment

Once at least 15 subjects have been treated in each of the five arms in Part 1, the SRC will review safety results separately for each arm in a blinded way every 2 weeks and evaluate causality. The study unblinded statistician will inform the SRC before their review if > 10% of the subjects in any arm meet any of the toxicity criteria listed below, without disclosing the arm(s). In case this criterion is met, the SRC will refer to the DSMB. The DSMB may recommend halting enrolment into arms of the same or longer duration with or without albendazole added and continuing enrolment in those arm(s) of the shorter duration, as shown in Table 1. The enrolment of the closed arms may be reopened using a lower dose of ABBV-4083 at 300 mg QD with the same duration and same combination (with or without albendazole) as the original arm, in which case enrolment will continue until 30 subjects have been enrolled at that dose. However, subjects who have already started to receive 400 mg QD ABBV-4083 in the halted arm and who have not experienced dose-limiting toxicity will remain on that dose until treatment completion.

When albendazole is used in mass drug administration programs, adverse events are commonly encountered in areas where gastrointestinal helminth infection occurs.⁷⁰ It is usually well tolerated and the liver injury reported with its use has been mild and self-limited in course.^{62,66,67,44} The proposed safety monitoring in the study includes blood counts and liver tests including transaminases and total bilirubin levels at treatment initiation and frequent monitoring during treatment. Furthermore, the proposed adaptive design of the study, allowing for arms with lower doses of ABBV-4083 if toxicity is observed in initial arms, will mitigate the potential risk of effects on the liver with co-administration of ABBV-4083 + albendazole.

The end of exposure is defined as one day after the last dose of IMP, which is at least five half-lives ($t_{1/2}$) after the last intake of IMP, i.e. ABBV-4083 or albendazole. The half-life of ABBV-4083 is less than 4 hours and the half-life of albendazole sulfoxide is 8-12 hours but active albendazole is administered up to Day 6 at the longest duration.

A subject will be considered to have a toxicity if they have:

- · an IMP-related treatment-emergent AE leading to discontinuation, i.e. considered as having a reasonable possibility of being related to any of the IMPs, and with onset between Day 0 and 30 days after the end of treatment;
- a severe or serious IMP-related treatment emergent AE, i.e. considered as having a reasonable possibility of being related to any of the IMPs, and with onset between Day 0 and 30 days after the end of treatment;
- a Grade 3 or 4 ALT elevation during treatment, defined as between Day 0 and 2 days after the end of treatment; ALT elevations will not additionally be counted as AEs described in the previous two criteria, although they may be reported as AEs.

The SRC and DSMB will continue to monitor the toxicity criteria in Part 2, and the safety results will be cumulative from Part 1 to Part 2. That is, subjects with an event meeting the toxicity criteria during Part 1 will still count in Part 2 for the same treatment, as if the study was not paused between Part 1 and Part 2. If > 10% of subjects in any regimen meet the toxicity criteria across Parts 1 and 2, the regimen will halt but dose adjustment will not occur in Part 2. Safety will be reviewed by the SRC and DSMB using the same criteria for any arms in Part 1 that are restarted using the 300 mg ABBV-4083 dose.

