3.5.2.3 Dose-adjusted Arms in the Event of Toxicity

If > 10% of subjects in an arm of Part 1 meet any of the toxicity criteria, the actions shown in Table 1 may be implemented. Decisions for dose reduction will be taken based on all available safety data including the events that trigger the dose adjustment process.

Table 1. Dose Adjustment Recommendations for Toxicity Management in Part 1		
Toxicity criteria	Recommended action	Rationale
reached in		

Toxicity criteria	Recommended action	Rationale
reached in		
Arm A or Week 1 of Arm B	Halt all study arms, then begin to enrol new Arm F, Arm G, Arm H and/or Arm I with a reduced dose of ABBV-4083 300 mg QD (n=30/arm), continue to enrol the remainder of Arm E in Arm J (to a total n=30).	Presumes that dose of ABBV-4083 is too high and that albendazole does not add to the observed toxicity.
Week 2 of Arm B	Halt Arm B, then begin to enrol new Arm G with ABBV-4083 300 mg QD (n=30)	Presumes that dosing ABBV-4083 400 mg QD is safe for 7 days but not 14 days.
Arm C	Halt Arm C, then begin to enrol new Arm H with ABBV-4083 300 mg QD (n=30)	Presumes that dosing ABBV-4083 + albendazole 400/400 mg QD is safe for 3 days but not 7 days.
Arm D	Halt Arms C and D, then begin to enrol new Arms H and I with ABBV-4083 300 mg (n=30/arm)	Presumes that dosing ABBV-4083 + albendazole 400/400 mg QD is not safe.

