#### 2.3 Treatment Assignment and Blinding

Subjects will be randomized continuously 1:1:1:1:1 into one of five parallel treatment arms through an Interactive Response Technology (IRT) system. Randomization will be

stratified by the number of operable sites with onchocercomata (one site vs. more than one site).

The five treatment arms are defined as follows:

- Arm A: 7 days of ABBV-4083 400 mg + albendazole matching placebo followed by 7 days of ABBV-4083 matching placebo
- Arm B: 7 days of ABBV-4083 400 mg + albendazole matching placebo followed by 7 days of ABBV-4083 400 mg
- Arm C: 7 days of ABBV-4083 400 mg + albendazole 400 mg followed by 7 days of ABBV-4083 matching placebo
- Arm D: 3 days of ABBV-4083 400 mg + albendazole 400 mg followed by 4 days of ABBV-4083 400 mg + albendazole matching placebo followed by 7 days of ABBV-4083 matching placebo
- Arm E: 7 days of ABBV-4083 matching placebo + albendazole 400 mg followed by 7 days of ABBV-4083 matching placebo

The treatment assignment will remain blinded to the Investigator, as well as clinical, pharmacy, and laboratory personnel, and the Sponsor, including statistics and data management personnel and the study monitor, until the final database lock, after all Part 1 subjects are followed to Month 6 or have prematurely discontinued from follow-up.

Toxicity of the treatments will be monitored throughout the study. If > 10% of the subjects in any arm meet any of the protocol-specified toxicity criteria after 15 subjects are enrolled in each arm, the Data and Safety Monitoring Board (DSMB) may recommend halting enrolment into arms of the same or longer duration with or without albendazole and continuing enrolment in those arms of the shorter duration. The enrolment of the closed arms may be reopened using a lower dose of ABBV-4083 at 300 mg QD with the same duration and same combination (with or without albendazole) as the original arm, in which case enrolment will continue until 30 subjects have been enrolled at that dose. However, subjects who have already received 400 mg QD ABBV-4083 in the halted arm

and have not experienced dose-limiting toxicity will be kept on the same dose until treatment completion.

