If Arm A, B, C, or D is closed and then reopened using ABBV-4083 at 300 mg QD, the subjects previously given ABBV-4083 at 400 mg QD in the closed arm will be excluded from all efficacy analyses (Section 9.1). Throughout this SAP, Arm A, B, C, D will be used to denote treatment regimens using either ABBV-4083 at 400 mg or 300 mg QD. For the actual treatment assignment, Arm A, B, C, D will be renamed as Arm F, G, H, I, respectively, upon reopening. For safety analyses, all arms will be summarized separately, even if any of them is closed during the study (Section 10.0). If all of Arms A, B, C, and D are closed, and any of Arms F, G, H, I are opened, the control arm (albendazole alone), Arm E, will be replaced with Arm J which uses the same pill count as Arms F, G, H, I to maintain blinding of the control arm. For all analyses, subjects from Arm E and Arm J will be combined.

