# 9.0 Efficacy Analyses

#### 9.1 General Considerations

The analyses for the primary endpoint will be conducted in both the PP population and the ITT population. However, the PP population will be the population used for the primary estimand comparisons. All other efficacy analyses will be conducted in the ITT population. The testing of the two primary hypotheses will be 2-sided at an alpha level of 0.10. No adjustment for multiple comparisons will be made.

The Primary Analysis will be performed after all subjects have completed the Month 6 Visit or have prematurely discontinued study follow-up. This will be the only and final analysis for the primary endpoint as well as all other efficacy endpoints.

If Arm A, B, C, or D is closed and then reopened using ABBV-4083 at 300 mg QD, only the new arm using 300 mg ABBV-4083 will be included in the efficacy analyses of this SAP. Efficacy summaries of the closed arms may be performed as ad hoc analyses.

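### If a 300 mg arm reopens and 1:1 allocation continues, about half or more of its 30 subjects enrol after the albendazole control arm is full

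*Protocol*

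**What the plan says.** Protocol 3.2 states that the 150 Part 1 subjects "will be randomised continuously 1:1:1:1:1 into one of five parallel treatment arms until group size is achieved", with 30 in Arm E.

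Protocol 3.5.2.2 starts the toxicity review "Once at least 15 subjects have been treated in each of the five arms in Part 1". SAP 2.3 words the gate slightly differently ("meet any of the protocol-specified toxicity criteria after 15 subjects are enrolled in each arm"). A closed arm may reopen at the lower dose, "in which case enrolment will continue until 30 subjects have been enrolled at that dose".

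Table 1 (Protocol 3.5.2.3) repeats the fresh 30. For week 2 of Arm B it reads "Halt Arm B, then begin to enrol new Arm G with ABBV-4083 300 mg QD (n=30", and the Arm C row has the same form with new Arm H. The Arm D row closes C and D and opens H and I. The row for Arm A or week 1 of Arm B halts every arm and opens F, G, H and/or I. Control is then not extended: "continue to enrol the remainder of Arm E in Arm J (to a total n=30".

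On analysis, SAP 9.1 says "only the new arm using 300 mg ABBV-4083 will be included in the efficacy analyses of this SAP", and SAP 2.3 says "For all analyses, subjects from Arm E and Arm J will be combined". The model in SAP 9.3.2 contains treatment arm only. The one supplementary analysis in SAP 9.3.3 repeats the same contrasts in the ITT population. Neither document gives an allocation ratio after reopening, a control top-up, a concurrent-control analysis or a term for enrolment period.

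**The concern.** The reopened arm starts from zero and needs 30 places. Control has at most 15 left. Under equal allocation the two cannot finish together, so the reopened arm ends with a run of subjects who have no albendazole subject randomised alongside them. For that run, allocation is no longer random with respect to control, and where only one arm is open it is predictable.

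A second weakness is separate. The reopened arm is compared with a pooled control group, part of which was enrolled before the halt, when the reopened arm did not exist. Any change over time in the subjects, the sites or the nodule material then enters the odds ratio. Sites recruit competitively (Protocol 3.1), so the site mix can shift.

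At stake are the Part 1 contrasts for the reopened regimen: proof of concept against Arm E and, where a combination arm alone is reopened, the combination-rule contrast with Arm A, which also fills to 30.

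**Working it through.** **Inputs.** Thirty per arm, equal allocation (Protocol 3.2); gate of 15 treated per arm and fresh 30 (3.5.2.2); E + J capped at 30 (Table 1); 70% v 30% of worms, ICC 0.54, the worm-count distribution, 17% dropout, two-sided α = 0.10 (Protocol 10.3.1).

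**The plan's own figures.** 25/(1 − 0.17) = 30.1, against 30 stated. Effective worms per subject = Σ p(m)·m/[1 + (m − 1)·0.54] = 1.406. With 17 × 1.406 = 23.9 effective worms per arm, the pooled-variance two-proportion formula gives 88.9% power, against 88% stated. The approximation is good enough for what follows.

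**Step 1: the tail.** With n per arm at the halt, control has 30 − n places and the reopened arm needs 30. At 1:1, control fills when the reopened arm holds 30 − n, so 30 − (30 − n) = n of its subjects remain.

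| n at halt | control places left | reopened subjects after control is full |
|---|---|---|
| 15 | 15 | 15/30 = 50% |
| 20 | 10 | 20/30 = 67% |
| 25 | 5 | 25/30 = 83% |

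These are expectations under balanced allocation. Simulating a halt at the earliest moment gave a mean of 15.7 (95% range 14 to 18) with blocks of 5 and about 16 (13 to 19) with blocks of 10. Without blocking the mean was about 20, with wide variation. If other arms keep enrolling between halt and reopening, n is the control count at reopening, and the share is larger.

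**Step 2: what the tail looks like by row of Table 1.**
- Arm B week 2, and Arm C: one arm is open, so nobody in the tail is randomised.
- Arm D: the tail is split only between H and I.
- All arms halted: F to I stay concurrent with each other, so H v F is unaffected, but the last n of each have no concurrent control.

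**Step 3: bias from pre-halt controls.** Suppose depletion shifts by d points at the halt and treatment has no effect. The reopened arm sits at p + d and the control pool at p + d(30 − n)/30. The difference is d × n/30. The value of d is an assumption.

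| d | n = 15 | n = 20 | n = 25 |
|---|---|---|---|
| 5 points | 2.5 | 3.3 | 4.2 |
| 10 points | 5.0 | 6.7 | 8.3 |

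Take 25 evaluable per arm (25 × 1.406 = 35.2 effective worms) and 30% depletion before the halt. The chance of false superiority, nominally 5% in that direction, is then about 8% (n = 15) to 10% (n = 25) for a favourable 5-point shift, and 11% to 18% for 10 points.

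**Step 4: does changing the ratio remove this bias?** Not for a step change: n of 30 controls still predate the halt. For steady drift, compare mean enrolment positions in the Arm C row at n = 15. At 1:1, control averages 75 and the reopened arm (15 × 112.5 + 15 × 157.5)/30 = 135, a gap of 60. With the ratio reset to places remaining, control averages (15 × 37.5 + 15 × 120)/30 = 78.75 and the reopened arm 120, a gap of 41.25, which is 31% less. At n = 20 the gap goes from 73.3 to 56.7 (23% less), and at n = 25 from 83.3 to 72.9 (12.5% less).

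**Step 5: a period term in the primary model.** In the all-arms row only E/J spans both periods, so such a term reduces each control contrast to the reopened arm v Arm J. Evaluable controls are 0.83 × (30 − n): about 12, 8 and 4. Power for 70% v 30% falls from 97% (25 v 25) to 89%, 80% and 59% with pooled variance, or from 98% to 91%, 83% and 62% unpooled.

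**The case against.** The strongest reply is contingency. The DSMB may recommend a halt, an arm may be reopened, and the ratio afterwards is simply unstated. Protocol 9.2.3 leaves randomisation detail to the Study Operations Manual, which is not available here. That stands as a limit on likelihood. It does not remove the point, because the ratio and caps that are written down give the weaker comparison.

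A reader might also infer more than the documents support:

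- *That the reopened regimen's contrasts all become historical.* In the all-arms row, H and F enrol together if both are opened, so that combination contrast stays randomised and concurrent.
- *That the tail is in effect open-label.* Predictable assignment weakens allocation and blinding, but the endpoint is immunohistology, nodules go to an external institute (Appendix 5), laboratory personnel stay blinded (7.4.1) and dosing is directly observed (7.6).
- *That Amendment 1 supplies the drift.* It was written with 57 randomised, about 11 per arm, whereas the gate needs at least 75 treated. If it took effect then, about 11.4/30 = 0.38 of controls predate it whatever n is, and a before/after-reopening split would not line up with it. Its effective date is not given, and the documents offer no reason why co-infection would change *Wolbachia* status in these worms.
- *That this odds ratio picks the Part 2 regimen.* Protocol 10.9 uses all available data, including safety and embryogenesis, and Part 2 enrols independent subjects with its own randomised comparator.
- *That a new ratio cures the bias, or that a period term belongs in the primary model.* Steps 4 and 5 show otherwise.

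**Conclusion.** The concern holds as a conditional design weakness. If a 300 mg arm is reopened, equal allocation continues and control stays capped at 30, about n of the 30 reopened subjects (n at least 15, so about half or more in expectation) enrol after control is full. In the Arm B week-2 and Arm C rows they are not randomised at all. The bias from pre-halt controls is a separate matter: about d × n/30 for a step change, under any ratio. Its size rests on an assumed d, and the formula takes worm counts and dropout as equal across periods. The affected contrasts are one input among several to Part 2 selection. The change is worth making because it is cheap and must be in place before any reopening.

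**What to change.** 1. In Protocol 3.5.2.2 and SAP 2.3, state that on reopening the allocation ratio is reset to the places remaining. After an Arm C halt at 20 per arm these are 10:10:10:10:30, so A:B:D:E:H = 1:1:1:1:3. In the all-arms row at 20 per arm they are 30:30:30:30:10, so F:G:H:I:J = 3:3:3:3:1. All arms then close together and every subject in the reopened arm is randomised alongside control.
2. In SAP 9.3.3, for contrasts involving a reopened arm, add a sensitivity analysis restricted to subjects randomised after reopening. Add a model adjusted for enrolment period as a further sensitivity analysis. Leave the primary model in SAP 9.3.2 unchanged.

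**Cost.** A randomisation list, which the new arms need anyway, and SAP wording; no extra patients. The first change removes the tail but not the bias from pre-halt controls. The second shows how far the result depends on those controls, but imprecisely: at most 15 concurrent controls, about 12 evaluable (15 × 0.83 = 12.45). The two changes help each other. At n = 15 the concurrent-only comparison has about 25 v 12 evaluable and 89% power under the reset ratio, against about 12 v 12 and 78% if 1:1 continues.
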